8. STATISTICAL ANALYSIS

8.1 General Data Handling Rules and Definitions

All data collected on CRFs will be provided in listings, except data collected only for confirmation of study entry criteria and for study administrative purposes. If any randomized subject is found to be without valid documented informed consent, that subject's data will be excluded from the report, except as necessary to document the error.

All statistical analyses will be conducted using SAS version 9.4 or newer.

Except where specified, all continuous variables will be summarized with descriptive statistics (the number of non-missing values, mean, standard deviation, median, minimum and maximum) and all categorical variables will be summarized with frequency counts and percentages, by treatment and treatment group. Unless otherwise specified, the mean and median will be displayed to 1 more decimal place than the original data, and standard deviation will be displayed to two more decimal places than the original data. All frequencies will be rounded to 1 decimal place.

Missing data will be maintained as missing unless specified otherwise. For variables where missing data is imputed, the analysis dataset will contain one variable with the imputed value and the original variable with missing maintained as missing.

8.2 Subject Disposition

An overall disposition table for all subjects will be presented. This tabulation will include the number of subjects randomized, treated, completed, and those who discontinued early from the study. The number and percentage of randomized subjects who are included in the PK, Safety and PD Populations will also be tabulated.

Subject disposition by treatment, and treatment sequence, will also be summarized. These tabulations will include the number of subjects dosed, completed, and those who discontinued early from the study along with the corresponding primary reasons for early termination.

Subjects in the Safety Population who prematurely discontinued from the study will be summarized by primary reason for early termination.

Subject disposition will be listed for all subjects in the Safety Population.

8.3 Demographic and Baseline Characteristics

Demographic and baseline characteristics will be summarized by treatment, and by treatment sequence, for both the Safety and PK Populations and listed.

Descriptive statistics (n, mean, median, standard deviation, minimum, and maximum) will be presented for continuous variables. Frequency distributions (counts and percentages) will be presented for categorical variables.

Medical history and baseline conditions will be summarized by treatment sequence and listed. Physical examination, as well as prior and concomitant medications, will also be listed. Prior and concomitant medications will be listed with the drug names and ATC classification codes based on the data collected in the eCRF. The World Health Organization (WHO) Drug Dictionary, version March 2016 or newer, will be used to classify prior and concomitant medications by therapeutic class and drug name.

Abnormalities in the subjects' medical and surgical histories will be coded using version 20.0 (or newer) of MedDRA Medical Dictionary for Regulatory Activities, and summarized and listed.

8.4 Safety Analyses

Safety analyses will be performed using the Safety Population, unless otherwise specified.

Safety measurements will include AEs, clinical laboratory tests (i.e. serum chemistry, hematology and urinalysis), ECGs, physical exams and vital signs. All safety data will be summarized by treatment. Baseline values for clinical laboratory tests, vital signs and ECGs will be defined as the last evaluation performed prior to administration of study drug.

8.4.1 Adverse Events

All AEs will be coded to system organ class (SOC), and preferred term (PT), using the latest Medical Dictionary for Regulatory Activities coding dictionary (version to be specified in the clinical study report). All reported AEs will be listed, but only TEAEs will be summarized.

The incidence of all TEAEs will be summarized by treatment. In the summary tables, subjects may be counted under multiple SOCs and PTs, but for each SOC and PT, subjects are only counted once. If a subject has the same AE on multiple occasions, the highest severity (severe > moderate > mild) or drug relationship (definite > probable > possible > not likely related > unrelated) recorded for the event will be presented. If severity is missing, subjects will be included as missing (for severity). If drug relationship is missing, subjects will be included in related tables (e.g., considered related). Summary tables will be organized by SOC, then PT.

The following summaries will be presented for TEAEs:

- Overall Summary of TEAEs by Treatment
- Incidence of TEAEs by Treatment, System Organ Class, and Preferred Term
- Incidence of Treatment Emergent Serious Adverse Events by Treatment, System Organ Class, and Preferred Term

Subjects who prematurely discontinued due to TEAEs and subjects with serious TEAEs will be listed.

8.4.2 Laboratory Data

Summary tables for laboratory parameters (including hematology, chemistry, and urinalysis) will be summarized for each treatment. Summaries for change from baseline for hematology, chemistry, and urinalysis parameters will include descriptive statistics (the number of non-missing values, mean, standard deviation, median, minimum and maximum) for values and change from baseline values for all continuous variables, and frequency counts and percentages for categorical variables, by treatment. Subjects with laboratory data outside the normal range will be listed with abnormal values flagged.

8.4.3 Vital Signs

Summary tables for vital signs data will include descriptive statistics (the number of non-missing values, mean, standard deviation, median, minimum and maximum) for values and change from baseline values by treatment.

A listing of vital signs results will be provided for all subjects in the Safety Population.

8.4.4 Electrocardiogram (ECG)

ECG parameters (RR interval, PR interval, QRS duration, QT interval, and QTcB interval) will be summarized by changes from baseline values by treatment and treatment group using descriptive statistics. For each parameter, only subjects who had both baseline and a post-baseline assessment will be included in the summary.

A listing of ECG results will be provided for all subjects in the Safety Population.

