 12. Subjects who have previously received exenatide, or any other GLP-1 RAs within three months from the screening or subjects who have had any GLP-1 RA and suffered an adverse reaction due to the medication.
 13. Subjects who had previously received EGT0001474 or EGT0001442, or any other SGLT2 inhibitors within 3 months from the screening.
 14. Subjects whose screening electrocardiogram (ECG) demonstrates any one of the following: heart rate > 100 bpm, QRS > 120 msec, QTc > 470 msec (corrected by Fridericia's formula), PR > 220 msec (a subject with PR > 220 msec will generally be excluded but exceptions may be allowed at the discretion of the investigator), or any clinically significant arrhythmia.
 15. Subjects whose sitting blood pressure is above 140/90 mmHg at screening. If the sitting blood pressure at screening is above 140/90 mmHg, one repeat measurement is allowed and the subject may be randomized if the blood pressure is 140/90 +/-5 mmHg at the discretion of the Investigator.
 16. Subjects who have a positive result of hepatitis B surface antigen (HBsAg), hepatitis C virus (HCV) antibody, urinary drug or urinary cotinine test.
 17. Subjects with human immunodeficiency virus (HIV) infection.
 18. Subjects who have had a febrile illness within 5 days prior to the first dose of study medication.
 19. Subjects vaccinated within 30 days (with the exception of the flu vaccine) prior to the first dose of investigational drug.
 20. Subjects with a history of acute or chronic pancreatitis or gall stones.
 21. Positive urine glucose at screening.
 22. Subjects with estimated glomerular filtration rate (eGFR) < 90 mL/min/1.73 m² or a history of kidney transplant.
 23. Subjects with digestion problems, including gastroesophageal reflux disease, irritable bowel syndrome, gastroparesis, and any other disorder deemed by the investigator to be clinically significant.

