6.5 Electrocardiography

6.5.1 12-Lead Electrocardiograms

A 12-lead electrocardiogram (ECG) will be conducted as listed in [Appendix 1](#) and whenever clinically indicated.

This procedure should be performed in the supine position after at least 10 min of rest. ECG parameters measured will be the RR interval, PR interval, QRS duration, and QT. Each ECG should also be assessed by the investigator for signs of ischemia, clinically significant hypertrophy, and clinically significant T-wave abnormalities.

It is the investigator or designee's responsibility to review the results of the ECG as they become available. For each abnormal ECG result, the investigator needs to ascertain if this is a clinically significant change from the screening ECG for that individual subject (this determination, however, does not necessarily need to be made the first time an abnormal result is observed. The investigator may repeat the ECG to verify the results of the original result). If the ECG result is determined to be a clinically significant and abnormal change from baseline for that subject, this is considered an AE.

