9.7.3 Clinical and Laboratory Events and Analyses

Clinical and laboratory metrics are measured at baseline and during the treatment. These variables include vital signs (blood pressure, respiration, temperature), clinical laboratory results (see [Section 6.6](#) for a complete list), and ECGs.

Serum chemistry, hematology, and urinalysis (quantitative parameters) data will be summarized for each treatment period. Summaries for change from baseline will be presented for these laboratory tests. In addition, all serum biochemistry, hematology, and urinalysis data outside the reference ranges will be summarized by parameter.

Laboratory data will be summarized using Low-Normal-High shift tables. ECG results will be summarized as changes from baseline in intervals. Abnormalities as well as changes from previous assessment will be listed.

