BLOQ	below the limit of quantitation
BMI	body mass index
BP	blood pressure
BUN	blood urea nitrogen
Ca	calcium
Cl	chloride
C _{last}	concentration corresponding to T _{last}
CL/F	apparent oral clearance
cm	centimeter
C _{max}	maximum observed plasma concentration
CRF	case report form
CV	coefficient of variation
DBP	diastolic blood pressure
DDI	drug-drug interaction
dL	deciliter
DM	data management

Abbreviation	Term
ECG	electrocardiogram
FDA	Food and Drug Administration
FPG	fasting plasma glucose
h	hour(s)
HBsAg	hepatitis B surface antigen
HCO ₃	Bicarbonate
Hct	hematocrit
HCV	hepatitis C virus
HDL-C	high density lipoprotein cholesterol
Hgb	hemoglobin
ICF	informed consent form
IRAE	immediately reportable adverse event
K	potassium
kg	kilogram
KR	Kenward-Roger
L	liter
λ_z	terminal elimination phase rate constant
LDL-C	low density lipoprotein cholesterol
LLN	lower limit of normal
LS	least square
MCH	mean corpuscular hemoglobin
MCHC	mean corpuscular hemoglobin concentration
MCV	mean corpuscular volume
MedDRA	Medical Dictionary for Regulatory Activities
mg	milligram
min	minute

Abbreviation	Term
mL	milliliter
msec	millisecond
Na	sodium
NCA	non compartmental analysis
NTR	not treatment related, includes unrelated
OHA	oral hypoglycemic agent
OTC	over the counter
PCS	potentially clinically significant
PD	pharmacodynamic
PE	physical examination
PK	pharmacokinetic
PR	The period that extends from the beginning of the P wave (the onset of atrial depolarization) until the beginning of the QRS complex (the onset of ventricular depolarization).
PT	preferred term
QA	quality assurance
QC	quality control
QRS	The combination of three of the graphical deflections seen on a typical electrocardiogram.
QT	Time from electrocardiogram Q wave to the end of the T wave corresponding to the electrical system
QTcB	QT corrected using Bazetts formula $[QT/(RR^{1/2})]$
RBC	red blood cell (count)
REML	restricted maximum likelihood
RR interval	intra-beat interval
SAE	serious adverse event
SAP	statistical analysis plan

Abbreviation	Term
SAS	statistical analysis software
SBP	systolic blood pressure
SD	standard deviation
SOC	system organ class
SOP	standard operating procedure
$T_{1/2}$	apparent terminal elimination half-life
TC	total cholesterol
TEAE	treatment emergent adverse event
TG	triglycerides
T_{last}	time of last measurable (positive) concentration
TLF	table, listing, figure
T_{max}	time of maximum observed plasma concentration

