6. SPECIFICATION OF ENDPOINTS AND VARIABLES

6.1 Demographic and Baseline Characteristics

Demographic variables consist of the following:

- Age in years (continuous) derived as the integer value of (informed consent date – date of birth + 1)/365.25
- Sex
- Race
- Ethnicity

Baseline characteristics consist of the following:

- Body mass index (BMI)

- Weight (kg)
- Height (cm)
- Vital signs
 - systolic blood pressure (SBP, mmHg)
 - diastolic blood pressure (DBP, mmHg)
 - oral temperature (°C)
 - pulse (beats per minute)
 - respiration rate
- Electrocardiogram (ECG) parameters
 - RR interval (msec)
 - PR interval (msec)
 - QRS duration (msec)
 - QT interval (msec)
 - QTcF interval (msec)
- Medical history and baseline conditions
- Clinical laboratory tests
- Prior and concomitant medication
- Physical examination

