6.3.6 Electrocardiogram

ECG parameters, including the RR interval (intra-beat interval), PR interval (the period that extends from the beginning of the P wave [the onset of atrial depolarization] until the beginning of the QRS complex [the onset of ventricular depolarization]), QRS duration, and QT interval (the corrected QT interval is the measure of the time between the start of the Q wave and the end of the T wave in the heart's electrical cycle), will be measured according to the study assessment schedule as specified in Section 3.6. Each ECG will be assessed by the Investigator for signs of ischemia, clinically significant hypertrophy, and clinically significant T-wave (repolarization of the ventricles) abnormalities. Baseline ECGs will be defined as the last evaluation performed prior to the administration of study drug in each treatment period.

ECG changes from baseline will be summarized by treatment.

Change from baseline to time point t, denoted Change_t, will be calculated as:

$$\text{Change}_t = \text{Value}_t - \text{Value}_{\text{Baseline}}$$

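### The SAP reports corrected-QT change only by Bazett although eligibility and the baseline list use Fridericia; secondarily, it sets no cut-off for related adverse events and omits the by-relationship outputs the protocol requires

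*SAP*

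**What the plan says.** **QT correction**

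- Protocol 4.3, exclusion 14, screens on "QTc > 470 msec (corrected by Fridericia's formula").
- SAP 6.1 has one corrected interval among the baseline ECG characteristics: "QTcF interval (msec").
- SAP 8.4.4 plans the change summary: "ECG parameters (RR interval, PR interval, QRS duration, QT interval, and QTcB interval) will be summarized by changes from baseline values". QTcF is not in it.
- The SAP glossary defines QTcB as "QT corrected using Bazetts formula", with the square root of RR as divisor. It has no entry for QTcF.
- Protocol 6.5.1 says "ECG parameters measured will be the RR interval, PR interval, QRS duration, and QT", so either correction has to be derived.
- Protocol 9.7.3 says only that "ECG results will be summarized as changes from baseline in intervals" and names no correction.

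SAP section 10, on changes from the protocol, does not mention or explain the different corrections.

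**Relatedness of adverse events**

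- Protocol 6.9 has five levels: definite, probable, possible, not likely and unrelated. Not likely means that no reasonable causal relationship exists.
- Protocol 9.7.1 treats an event as drug-related when the relationship is possible or stronger. It asks for a listing of such treatment-emergent events and for tabulations by relationship.
- The SAP glossary puts the not-likely level in TR (treatment related) and names only unrelated under NTR.
- SAP 8.4.1 sends subjects with a missing relationship to the related tables, but does not say which of the five levels count as related. It names three summaries: overall, by system organ class and preferred term, and the same for serious events. None is described as by relationship, and the related-event listing is not named.

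**The concern.** Safety and tolerability of the combination is the secondary objective, and the ECG and adverse-event tables are its main output.

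For QT, the baseline table would show one corrected interval and the change table another. The reader could not set a reported change beside the reported baseline, nor beside the scale on which subjects were admitted. The two corrections separate whenever heart rate moves, so a heart-rate shift alone can make one change column move while the other stays still.

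For adverse events, a programmer looking for the meaning of related would find only one grouping of the five levels in the SAP, and that grouping contradicts the protocol. If it reached an output, the drug-related count would include events that the protocol's own definition says lack a reasonable causal relationship. Apart from that, two outputs that the protocol asks for have no home in the SAP.

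**Working it through.** **1. Relation between the two corrections**

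The inputs are the Bazett form from the SAP glossary, QTcB = QT / RR^(1/2), and the standard Fridericia form, QTcF = QT / RR^(1/3). The protocol names the latter without printing it. RR is in seconds, so RR = 60 / HR.

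Substituting QT = QTcF × RR^(1/3):

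QTcB = QTcF × RR^(1/3 − 1/2) = QTcF × RR^(−1/6) = QTcF × (HR/60)^(1/6)

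The two agree only at 60 bpm.

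**2. Illustration of a change from baseline**

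The documents give no post-dose QT or heart-rate figure and predict no heart-rate change, so there is no plan figure to reproduce. All inputs here are assumed: QTcF constant at 400 ms and heart rate from 60 to 70 bpm.

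| | 60 bpm | 70 bpm | Change |
|---|---|---|---|
| RR (s) | 1.000 | 60/70 = 0.857 | |
| QT = 400 × RR^(1/3) (ms) | 400.0 | 380.0 | −20.0 |
| QTcF (ms) | 400.0 | 400.0 | 0 |
| QTcB = 400 × (HR/60)^(1/6) (ms) | 400.0 | 410.4 | +10.4 |

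Range with QTcF held at 400 or 420 ms and baseline heart rate at 60, 65 or 70 bpm:

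| Rise in heart rate | Change in QTcB | Change in QTcF |
|---|---|---|
| 3 bpm | +2.9 to +3.4 ms | 0 |
| 5 bpm | +4.7 to +5.6 ms | 0 |
| 10 bpm | +9.2 to +10.9 ms | 0 |

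The calculation is symmetric. If QTcB is held at 400 ms over the same 60 to 70 bpm, QTcF goes to 400 / (70/60)^(1/6) = 389.9 ms, a fall of 10.1 ms. The figures therefore show that the two summaries differ, not which of them is right.

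**3. Units**

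SAP 6.1 lists RR in msec. Both formulas need seconds. At 60 bpm, entering RR as 1000 instead of 1 would divide QT by 1000^(1/2) = 31.6 (Bazett) or 1000^(1/3) = 10 (Fridericia). The glossary does not state the unit.

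**4. Relatedness, side by side**

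| Level | Protocol 9.7.1 | SAP glossary |
|---|---|---|
| Definite, probable, possible | Related | TR |
| Not likely | Not related | TR |
| Unrelated | Not related | NTR |

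The two differ on one level only. Protocol 9.7.1 expects 20 subjects under each treatment. If an output used the glossary grouping, each subject whose only event is not likely related would add 1/20 = 5.0 percentage points to the related rate for that treatment.

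**The case against.** **No protocol analysis rule is broken.** This stands. A reader might infer that QTcB violates the protocol. It does not, because the protocol's analysis section names no correction and its list of measured parameters contains none. The defect is that the SAP's baseline list does not match its change summary, nor the correction chosen for eligibility.

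**Other readings that the documents do not support.**

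- Protocol 6.5.1 says that for each abnormal ECG "the investigator needs to ascertain if this is a clinically significant change from the screening ECG for that individual subject". A reader might take this to tie post-dose review to Fridericia. The sentence concerns clinical judgement for adverse-event reporting and names no correction. SAP 6.3.6 also uses a different baseline, the last ECG before study drug in each period.
- A reader might re-express the eligibility limit on the Bazett scale and conclude that subjects would appear to exceed it. SAP 8.4.4 has no threshold or outlier category, so nobody would be flagged.
- SAP 6.3.6 has "QT interval (the corrected QT interval is the measure of the time between the start of the Q wave" in its list of parameters. This is a slip of wording and does not make QT a corrected interval.

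**The information is not lost.** Changes in RR and uncorrected QT are also summarised, and ECG results are listed for every subject, so a heart-rate shift would be visible. This limits the harm. But the corrections are not linear in RR, so a mean QTcF change cannot be recovered exactly from the tabulated means. It has to be rebuilt from the individual data.

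**The TR and NTR entries may be leftover template text.** The SAP body never uses them. SAP 6.3.3.6 and 8.4.1 keep all five levels, and SAP section 1 says that the SAP is to be read with the protocol. A reader might infer that the drug-related counts will be wrong. The documents do not show that, because the table shells are a separate document that is not available here. What remains is firmer: SAP 8.4.1 relies on related tables without a cut-off, and does not name the outputs that Protocol 9.7.1 requires.

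**The replacement rule does not set a denominator.** A reader might use the minimum of 8 evaluable subjects per group in Protocol 5.4 to enlarge the effect per subject. Adverse-event percentages use the Safety Population by treatment received, so that floor is not the denominator.

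**Conclusion.** The QT point holds as an internal inconsistency: eligibility and baseline are on the Fridericia scale, and the only corrected-QT change summary is on the Bazett scale. Its size depends on heart-rate change. It is zero if heart rate does not move, and about 10 ms for an assumed rise of 10 bpm from 60 bpm. That figure rests on assumed values and says nothing about which correction is better.

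The relatedness point is secondary. The contradiction between the glossary and Protocol 9.7.1 is certain, but its effect is conditional on an output using the glossary grouping. The 5.0 points per subject assume that all 20 subjects are dosed under each treatment. The absence of the by-relationship tabulation and the related-event listing from SAP 8.4.1 does not depend on that condition, although the shells may contain them.

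Both points concern descriptive safety reporting only, and no PK or PD result changes. They should be corrected before the SAP is finalised, as matters of consistency.

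**What to change.** **QT**

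- In SAP 8.4.4, summarise change from baseline in QTcF, derived from the QT and RR already collected. QTcB may stay as a supplement.
- List the same correction or corrections in SAP 6.1, so that each change has a baseline on its own scale.
- Add QTcF = QT / RR^(1/3) to the glossary and state that RR is in seconds for both formulas.

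**Relatedness**

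- In the glossary, define TR as definite, probable or possible, and NTR as not likely or unrelated.
- In SAP 8.4.1, state that related means this TR group, and keep the existing rule that a missing relationship counts as related.
- Add to SAP 8.4.1 the tabulation of treatment-emergent events by relationship and the listing of those with a possible or stronger relationship.
- Check that the table, listing and figure shells match.

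**Cost:** a few lines of SAP text, one derived variable, one table, one listing and a check of the shells. QT, RR and the five-level causality assessment are already collected, so no new data are needed.
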